11.3. DOCUMENTATION REQUIRED PRIOR TO INITIATION

In addition to the documents mentioned in Sections 10.1 and 12.1, the following will be required from the Investigator prior to the initiation visit:

- Current, signed and dated Curriculum Vitae of Principal Investigator and any Sub-Investigators/co-workers,
- Normal ranges of all laboratory tests to be performed at the study site and a recent certification or accreditation of established quality control (or other documentation of established quality control or external quality assessment or other validation),
- A signed original of the final protocol and any amendments,
- Indemnity / certificate of Insurance,
- A signed original of the study Financial Agreement/Clinical Study Agreement with Dompé, including Pharmacy, radiology etc (i.e. all study specific costs),
- Form 1572 (USA and Canada), Qualified Investigator Undertaking, Research Ethics Board Attestation, Clinical Trial Site Information Form (Canada only),
- Financial disclosure form 3455 from all persons listed on the 1572,
- Data protection form (HIPAA in USA) signed by the Investigator (giving the Investigator's approval and the patient's consent for personal data to be kept on file at PPD),
- List of delegated responsibility (Study Team Signature List / Delegation of Responsibilities form).

11.4. DOCUMENTATION REQUIRED DURING THE STUDY

The following will be required from the Investigator during the study:

- Current, signed and dated Curriculum Vitae of Principal Investigator and any Co-Investigators/co-workers who are delegated protocol related responsibilities after study initiation,
- Updates of normal ranges (including the dates from which they become effective) of all laboratory tests to be performed at the study site and updates in certification or accreditation of established quality control (or other documentation of established quality control or external quality assessment or other validation),
- A signed original of any protocol amendments,
- Copies of any new approvals from or correspondence with the IRB/REB,
- Renewals of certificates of Insurance, as applicable per country regulations,
- Updated form 1572 (USA and Canada), Qualified Investigator Undertaking, Research Ethics Board Attestation, Clinical Trial Site Information Form (Canada only),
- Financial disclosure form 3455 from all **new** persons listed on the 1572,
- Updated list of delegated responsibility (Study Team Signature List / Delegation of Responsibilities form).

11.5. ESSENTIAL DOCUMENT RETENTION

The Investigator will retain copies of all the essential documents (as defined by ICH-GCP) until at least 2 years after the last approval of a marketing application in an ICH region, and until there are no pending or contemplated marketing applications in an ICH region, or at least 2 years have elapsed since the formal discontinuation of clinical development of the Investigational Product. These documents should be retained for a longer period however if required by the applicable regulatory requirements. The Investigator should take measures to prevent accidental or premature destruction of these documents.

The essential documents include at least: the signed protocol, copies of the completed CRFs, signed Patient Informed Consent Forms from all patients who consented, hospital records, and other source documents, IRB/REB approval and all related correspondence, including approved documents, and all other documentation included in the Investigator Site File and Pharmacy/Dispensing File.

The Investigator will inform PPD of the storage location of these essential documents and must contact PPD before disposing of any. If the Investigator wishes to assign the files to someone else or to remove them to another location, the PPD Medical Director should be consulted about this change.

Dompé will inform the Investigator in writing when these documents no longer need to be retained.

12. STUDY MANAGEMENT

The study will be performed in accordance with the protocol, the Declaration of Helsinki (Appendix 5), and ICH Harmonised Tripartite Guideline for Good Clinical Practice (*ICH-GCP*) and any local regulations.

12.1. REGULATORY BODY APPROVAL

The study will not be started until full written approval from the relevant regulatory body (FDA and Health Canada) has been received by Dompé. PPD will then provide the Investigator with a copy of appropriate document on behalf of Dompé.

PPD undertakes to obtain (on behalf of Dompé) the necessary approval from the Health Canada prior to initiation of the study. The responsibility for gaining FDA approval lies with an independent regulatory consultant employed by Dompé.

12.2. STAFF INFORMATION & RESPONSIBILITIES

It is the responsibility of the Investigator to ensure that all personnel involved in the study are fully informed of all relevant aspects of the study, including detailed knowledge of and training in all procedures to be followed.

The Investigator will provide a list of delegated responsibility to PPD detailing the various study tasks to be performed by each member of his/her study staff. Each staff member should sign in agreement to their performing each of the tasks delegated to them on the list.

12.3. MONITORING

Monitoring will be carried out by PPD, according to the current version of PPD SOP.

Prior to study start, the Investigator will be informed of the anticipated frequency of the monitoring visits. He/she will also receive a notification prior to each monitoring visit during the course of the study. It is expected that the Investigator and/or his/her sub-Investigator(s) and other appropriate staff will be available on the day of the visit to discuss study conduct and to cooperate with the monitor to ensure that any problems detected during the course of these monitoring visits are resolved.

The purpose of the monitoring visit is to verify that the rights and the wellbeing of the patient are protected, that the reported data are accurate, complete and verifiable from source documents and that the conduct of the trial complies with the currently approved protocol and any amendments, with ICH GCP, and with regulatory requirements.

The CRA will complete a standard report following each Monitoring Visit and provide this report to the Project Leader for review within a specified timeframe.

12.3.1. Access to records

The Investigator will allow designated PPD representatives, designated Dompé representatives, and regulatory bodies to have direct access to the source documents to verify the data reported in the CRFs. Source documents are the originals of any documents used by the Investigator or hospital/institution that allow verification of the existence of the patient and substantiate the integrity of the data collected during the trial. Source documents should be available to support all the data recorded in the CRF. Location of source data, including those for which the CRF might be accepted as being the sole source document, will be specified and listed at the center Initiation Visit.

12.4. AUDIT AND INSPECTION

Audit activities will be performed by PPD Quality Assurance group, except for audit of Protocol/Amendments, Patient Informed Consent Document, and CRF, which will be performed by the Dompé Quality Assurance Unit.

On one or more occasions the study site may be audited by PPD. The Investigator will be informed in advance of such a visit. All audits will be performed by PPD personnel according to the current version of PPD SOP.

Additionally the study site may be inspected by Dompé representatives or a regulatory agency on one or more occasions.

12.5. PROTOCOL DEVIATIONS/AMENDMENTS

Changes to the Protocol will be implemented only when written amendments have been signed by all individuals who signed the protocol.

Any amendment will be sent to the appropriate IRB/REB. No deviations from or changes to the protocol will be implemented without documented approval of an amendment from the IRB/REB which granted the original approval, except where necessary to eliminate an immediate hazard(s) to trial patient, or when the change(s) involves only logistical or administrative aspects of the trial. The deviations from or changes to the protocol implemented to eliminate an immediate hazard to the trial patient and the proposed amendment, if appropriate, should be submitted to the IRB/REB for review and approval as soon as possible.

Any other deviation from the protocol that has not been approved by PPD and the IRB/REB could result in a discontinuation from the study at the center involved.

Any written amendment will be sent to all recipients of the protocol and to the regulatory authorities (FDA/Health Canada).

12.6. DISCONTINUATION OF THE STUDY

Dompé reserves the right to stop the study at any time on the basis of new information regarding safety or efficacy, or if study progress is unsatisfactory, or for other valid administrative reasons. After such a decision is made, the Investigator must inform all relevant persons e.g. study staff, potential patients etc. within 2 weeks. All delivered study materials must be collected and all CRFs completed to the extent possible.

Study discontinuation will be notified to FDA/Health Canada within 5 days from decision.

12.7. PUBLICATIONS

Any manuscript, abstract or other publication or presentation of results or information arising in connection with the study must be prepared in conjunction with Dompé and must be submitted to the Dompé Medical Director for review and comment at least 45 days prior to submission for publication or presentation.

14. APPENDICES

14.1. APPENDIX 1 - METHODOLOGICAL DETAILS

14.1.1. PGD score - ISHLT system for grading of severity of primary graft dysfunction [*Christie et al, 2004*]

Grade 0	$\text{PaO}_2/\text{FiO}_2 \geq 300$ mmHg; no radiographic infiltrates
Grade 1	$\text{PaO}_2/\text{FiO}_2 \geq 300$ mmHg + radiographic infiltrates consistent with pulmonary oedema
Grade 2	$200 \text{ mmHg} \leq \text{PaO}_2/\text{FiO}_2 < 300$ mmHg + radiographic infiltrates consistent with pulmonary oedema
Grade 3	$\text{PaO}_2/\text{FiO}_2 < 200$ mmHg + radiographic infiltrates consistent with pulmonary oedema

Any patient with no infiltrate on chest X-rays is automatically grade 0, regardless of $\text{PaO}_2/\text{FiO}_2$ value. If the patient is on nasal cannula for oxygen or $\text{FiO}_2 < 0.3$, the patient is graded as 0 or 1, based on chest X-rays. Any patient on extra corporeal membrane oxygenation is automatically grade 3. Any subject mechanically ventilated with FiO_2 greater than 0.5 or requiring nitric oxide beyond 48 hours from the time of transplant should be considered grade 3.

If multiple blood gas values are available, the worst $\text{PaO}_2/\text{FiO}_2$ ratio will be used for the purpose of this grading scheme.

PGD score will be evaluated at the following time points:

- Time-0 (T0): defined as within 6 hours of final lung reperfusion. The first blood gas in ICU is ideal for this. Ideally, measurement should be done on $\text{FiO}_2 1.0$ and PEEP =5 while still on mechanical ventilation.
- T24, T48, T72: Later times being measured at potentially multiple time points after 24 hours, up to 72 hours. Time will be measured following $T0 \pm 6$ hours.

Chest X-rays will be graded by an Investigator, and then validated by a (blinded) transplant radiologist.

In patients with clinical diagnosis of PGD additional time points will be considered up to the clinical recovery of the condition as per available data according to center standard of care.

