6.5.3. Other treatments

Nitric Oxide, Surfactant, Prostaglandin E1 will be administered as per center practice.

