#### PGD Score

This is graded as an integer between 0 and 3 according to the following definitions:

Grade 0	no radiographic infiltrates
Grade 1	$\text{PaO}_2/\text{FiO}_2 \geq 300$ mmHg + radiographic infiltrates consistent with pulmonary oedema
Grade 2	$200 \text{ mmHg} \leq \text{PaO}_2/\text{FiO}_2 < 300$ mmHg + radiographic infiltrates consistent with pulmonary oedema
Grade 3	$\text{PaO}_2/\text{FiO}_2 < 200$ mmHg + radiographic infiltrates consistent with pulmonary oedema

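### The protocol's PGD override rules have no order of precedence and the SAP omits the grade 3 ones, so a patient on ECMO with a clear film can be graded 0 or 3

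*Protocol*

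**What the plan says.** Protocol Appendix 1, section 14.1.1, grades PGD from 0 to 3 by film and PaO2/FiO2 ratio, then adds rules that override the table:

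- **Clear film:** "Any patient with no infiltrate on chest X-rays is automatically grade 0". The sentence goes on to say that this holds whatever the PaO2/FiO2 ratio.
- **ECMO:** "Any patient on extra corporeal membrane oxygenation is automatically grade 3".
- **Prolonged support:** a subject ventilated with FiO2 above 0.5 "or requiring nitric oxide beyond 48 hours from the time of transplant should be considered grade 3".

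Neither grade 3 rule requires an infiltrate. The only tie-break in the section begins "If multiple blood gas values are available, the worst". It chooses among blood gases, not among rules. Nitric oxide is left to each site: "Nitric Oxide, Surfactant, Prostaglandin E1 will be administered as per center practice" (Protocol 6.5.3).

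SAP section 5 (PGD Score) says "This is graded as an integer between 0 and 3 according to the following definitions" and gives four rows. Grade 0 is "no radiographic infiltrates" and nothing else. Grades 1 to 3 need infiltrates and are separated by the ratio. ECMO, FiO2 above 0.5 and nitric oxide do not appear. SAP 1.2 (Changes from Protocol) records none.

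The score is tested by Cochran-Mantel-Haenszel methods at 0, 24, 48 and 72 hours (Protocol 9.4.3; SAP 9.5.2.2). It is one of the four secondary endpoints to which the protocol synopsis applies inferential tests.

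**The concern.** A patient on ECMO whose film is clear meets two rules in the same appendix, both worded as automatic, that assign opposite ends of the scale. A patient with a clear film who is still on nitric oxide beyond 48 hours meets a similar pair, although the grade 3 rule there is worded more softly. Two graders who follow the appendix can give different grades to the same data.

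The SAP table does give a single grade, but by leaving out the protocol's grade 3 rules without saying so. Read literally, it puts a patient on ECMO with a clear film in the best category.

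The grade also governs data collection. Protocol 7.5.2 treats diagnosed PGD as clinically recovered once the score is 1 or less, and additional PGD data are collected until then. A diagnosed patient still on ECMO whose film clears is recovered under one rule and grade 3 under the other.

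**Working it through.** The plan states no figure on this point, so there is none to reproduce. The check sets the two definitions side by side for each type of patient. *Support rule* means ventilation with FiO2 above 0.5, or nitric oxide, beyond 48 hours.

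| Film | Support | PaO2/FiO2 (mmHg) | Protocol 14.1.1 | SAP section 5 |
|---|---|---|---|---|
| Clear | Neither | Any | 0 | 0 |
| Clear | ECMO only | Any | 0 and 3 | 0 |
| Clear | Support rule only | Any | 0 and 3 | 0 |
| Clear | Both | Any | 0 and 3 | 0 |
| Infiltrates | ECMO | 300 or more | 3 (override) | 1 |
| Infiltrates | ECMO | 200 to below 300 | 3 (override) | 2 |
| Infiltrates | ECMO | Below 200 | 3 | 3 |

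**Clear film.** With three ratio bands and three support patterns (ECMO, support rule, both), there are 3 × 3 = 9 combinations. The protocol assigns both 0 and 3 in all 9. The SAP assigns 0 in all 9. Without ECMO or the support rule, both documents give 0 in all three bands.

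**Infiltrates.** The protocol's ECMO rule gives 3 at any ratio. The SAP gives 3 only when the ratio is below 200. Here there is no clash within the protocol. The SAP simply departs from it.

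**Time points.** The ECMO rule has no time limit, so its conflict can arise at 0, 24, 48 or 72 hours. The nitric oxide rule applies only beyond 48 hours from transplant, so it cannot affect the grades at 0 or 24 hours. The sentence does not make clear whether the 48-hour limit also applies to FiO2 above 0.5.

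**Size per patient.** Protocol 3.1 gives 100 patients randomized 1:1, or 50 per arm. Assume that all 50 have a grade at the time point.

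- Clear film, 0 versus 3: change in mean grade = 3/50 = 0.06; change in grade 3 share = 1/50 = 2 percentage points.
- ECMO with infiltrates, ratio 300 or more, 1 versus 3: 2/50 = 0.04 in the mean and 2 points in the share.
- ECMO with infiltrates, ratio 200 to below 300, 2 versus 3: 1/50 = 0.02 in the mean and 2 points in the share.
- ECMO with infiltrates, ratio below 200: no change.

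The mean grade is used here only to show scale. The SAP's table shell reports counts and percentages by grade.

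**The case against.** The best defense is the end of the clear-film sentence. By saying that the rule holds whatever the ratio, it may be meant only to relax the ratio requirement in the protocol's grade 0 row. On that reading it does not address ECMO, and the later, more specific ECMO sentence prevails. This is a reasonable reading, though the text does not compel it. It does not rescue the plan: if ECMO prevails, the SAP table misgrades these patients. If the clear film prevails instead, the ECMO sentence has no effect for them, and the SAP still misgrades patients on ECMO with infiltrates and a ratio of 200 or more.

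The SAP table yields one grade per patient, so it is not itself ambiguous. That stands, and it makes the mismatch between the documents the larger defect for the analysis. SAP 1.1 asks that the plan be read with the protocol, but a programmer who does so meets the unranked rules again.

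The protocol adopts a published consensus score that may settle the order. That cannot be checked from these documents, and neither carries such an order over.

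It also stands that only the clear-film and ECMO rules are worded as automatic, that the third covers specific support rather than any support, and that the endpoint is secondary and labeled exploratory (Protocol 4.2.1.2).

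**Conclusion.** The point holds. The protocol does not rank its override rules, and the SAP omits the grade 3 ones while declaring no changes. Each affected patient moves by up to 3 grades, or up to 0.06 in mean grade and 2 percentage points in grade 3 share for a fully graded arm of 50.

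The total effect cannot be sized, because the documents do not say how often ECMO or prolonged nitric oxide coincides with a clear film, or how often ECMO coincides with infiltrates and a ratio of 200 or more. Three stronger conclusions are tempting but unsupported:

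- **A large relative change in the grade 3 count.** A reader might take the reperfusion injury rate in Protocol 2.4 as 5 to 10 grade 3 patients per arm (10% to 20% of 50) and suppose a few clashing patients. The protocol gives that rate as an upper range, does not equate it with grade 3, and gives no count of clashing patients.
- **That these patients carry most of the information on PGD severity.** Nothing in the documents shows this.
- **That the main result is at risk.** The primary PaO2/FiO2 analysis does not use the PGD score.

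**What to change.** Reconcile Protocol 14.1.1 and SAP section 5 before database lock, while the study is blinded:

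1. Restore the protocol's override rules to the SAP definition.
2. State one precedence in both documents, with the ECMO rule applied before the clear-film rule. This respects the stated scope of the clear-film sentence, which names only the ratio as what it overrides. It is a scoring rule and does not touch patient care.
3. State how the beyond-48-hour rule ranks against a clear film, and whether the 48-hour limit covers FiO2 above 0.5 as well as nitric oxide. Say which FiO2 counts, since ventilated patients are turned to FiO2 = 1 for the study blood gas (Protocol 7.5.2).
4. Report one sensitivity table with the other order for all clear-film patients who meet that rule, by FiO2 or by nitric oxide.

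The cost is a short text change, one table and a data check. Protocol 6.5 records only number, name, indication and start date for most concomitant drugs, 7.3 lists nitric oxide use as an operative detail, and the ICU assessments in 7.5 do not name ECMO. The sponsor should confirm that the CRF captures ECMO status at each grading and the duration of nitric oxide.

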6.5. CONCOMITANT THERAPY

Any medications required for the patient's welfare are permitted and will be given at the discretion of the Investigator, except for drugs described in paragraphs below.

Administration of all prior and concomitant medications, apart from the agents listed below, from the time of enrolment until 10 days after the end of study drug administration or until hospital discharge (whichever occurs earlier) will be reported in the appropriate section of the CRF. For the intervals between 10 days or hospital discharge up to 12 month visit, only medications used for immunosuppression, prophylaxis of infections, and AE that the Investigator assesses as at least possibly related to the Investigational Product will be reported.

All the details as per the CRF fields (sequential number, drug name, indication, starting dose, doses at month 1, 6, and 12, route of administration, start/stop dates) will be recorded for the medications used for immunosuppression and prophylaxis of infections. Only the sequential number, the drug name, the indication and the start date will be recorded for all the other concomitant medications.

The following agents do not need to be recorded:

- Saline and other hydration solutions (including additional electrolytes)
- TPN and enteral feeds
- Homeopathic medications
- Elective vitamins and minerals
- Topical agents (apart from inhaled) with no or negligible systemic absorption
- Osmotic laxatives and locally acting antacids

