7.3. OPERATIVE COURSE

In principle, standard surgery procedures, excluding possible graft reflush with leukocyte depleted blood, will be applied as per center practice. However, it is suggested to adopt whenever possible, the following strategies:

- Application of topical hypothermia during implantation.
- After implantation, blood flow will be progressively, in a controlled way, restored over a period of up to 10 minutes (minimum 2 min).
- Protective ventilation strategy will be adopted during the initial period of reperfusion. It is suggested that the newly implanted lung allograft is gently reinflated with a sustained airway pressure of 20 cmH₂O before reperfusion and then ventilated with FiO₂ of 50%, PEEP =5 cmH₂O, and pressure control ventilation limiting peak airway pressures to 20 to 25 cmH₂O. After reperfusion has occurred, changes of ventilation will be directed by the anesthesiologist according to his/her judgment of the functional status of the implanted lung.

Relevant operative details will be recorded in the CRF, including gross abnormalities of the donor lung(s), duration of cold and warm ischemia, time of reperfusion, use and duration of cardiopulmonary bypass, lung reduction procedures, anastomotic difficulties, hypoxemia, and pulmonary edema, use of nitroglycerin/nitric oxide/inhaled prostacyclin/surfactant.

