7.5.2. Assessment in the ICU

The following will be assessed during ICU stay and recorded in the CRF, apart from SVR and PVR which will be calculated during data-management. Measurement will be performed as per center practice, unless otherwise specified. For the purpose of this study, clinically diagnosed PGD is defined as:

- An episode of decreased $\text{PaO}_2/\text{FiO}_2$ ratio and chest X-ray results consistent with a PGD score of grade 3, which is not the result of some other secondary cause of graft dysfunction [Christie, 2005]. When diagnosed, the condition is considered clinically recovered for a PGD score of ≤ 1 .
- $\text{PaO}_2/\text{FiO}_2$ ratio. $\text{PaO}_2/\text{FiO}_2$ ratio will be measured at $\text{FiO}_2 = 1$ q24 hours, up to extubation or up to 72 hours after ICU admission, whichever occurs earlier. Patients on $\text{FiO}_2 < 1$ will be turned back to $\text{FiO}_2 = 1$ for 5 minutes before gas measurement. Additional $\text{PaO}_2/\text{FiO}_2$ ratio values obtained as per center standard of care in patients with clinical diagnosis of PGD will be recorded in the CRF up to the clinical recovery of the condition.
- Chest X-rays. A chest X-rays will be obtained 24 hours, 48 hours, and 72 hours after ICU admission (see Appendix 1 for details).
- BP, HR. Vital signs will be measured q12 hours up to ICU discharge or up to 5 days after ICU admission, whichever occurs earlier.
- CO, PA pressure, SVR, PVR, PCWP, CVP. Cardiopulmonary physiologic measurements will be assessed q12 hours when a PA catheter is present, up to ICU discharge or up to 5 days after ICU admission, whichever occurs earlier. Additional measurements obtained as per standard of care in patients with clinical diagnosis of PGD will be recorded in the CRF up to the clinical recovery of the condition.

For all measurements above, the actual date and time of assessment will be recorded in the CRF.

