### 9.5.2.2 PGD score

Analysis of PGD score will be performed separately at time 0 and at 24, 48 and 72 hours after ICU admission. Two analyses, using Cochran-Mantel-Haenszel statistics from PROC FREQ within SAS, will be performed at each time point. The first will use type of transplant (single or double) as a stratification factor and will use the following SAS code:

```
Proc freq data=data1 (where=(time=x)) noprint ;  
  table tran_typ*PGD*treat/cmh out=ct_typ ;  
  output out=cmh type cmh ;  
run ;
```

As the randomization did not include type of transplant it is possible that there will be insufficient data within each of the cells to perform the analysis. This will be assessed after the Month 1 database lock.

The second analysis will use center as a stratification factor.

Both analyses will be performed for both the ITT and PP populations. For each analysis, the number and percentage of patients within each table cell will be presented, together with the second of the three p-values provided by PROC FREQ (labeled as Row Mean Scores Differ), and the corresponding Mantel-Haenszel odds ratio and the associated 95% confidence interval.

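### The PGD grading rules that depend on respiratory support cannot be reliably applied beyond 48 hours from the data the protocol lists, and the SAP omits them without declaring a change

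*Protocol*

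**What the plan says.** **Grading rules.** Protocol Appendix 1 (14.1.1) sets grades from the PaO2/FiO2 ratio and the chest X-ray, then adds rules that depend on support. A patient ventilated with FiO2 above 0.5 "or requiring nitric oxide beyond 48 hours from the time of transplant should be considered grade 3". A patient on nasal cannula, or with FiO2 below 0.3, can only be grade 0 or 1. A patient without infiltrates is grade 0 whatever the ratio.

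**Blood gas.** Under Protocol 7.5.2 the ratio is measured at FiO2 = 1 every 24 hours until extubation or 72 hours. Patients on less are put back to 1 "for 5 minutes before gas measurement".

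**Nitric oxide.** Protocol 6.5.3: "Nitric Oxide, Surfactant, Prostaglandin E1 will be administered as per center practice". Protocol 7.3 includes "use of nitroglycerin/nitric oxide/inhaled prostacyclin/surfactant" among the operative details to record. Protocol 6.5 asks for stop dates only for immunosuppression and infection prophylaxis. Otherwise: "Only the sequential number, the drug name, the indication and the start date will be recorded for all the other concomitant medications". The list of agents exempt from recording includes "Topical agents (apart from inhaled) with no or negligible systemic absorption", so inhaled drugs are not exempt under that item.

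**SAP.** Section 5, PGD Score: "This is graded as an integer between 0 and 3 according to the following definitions". Those definitions use only the ratio and infiltrates. Section 9.5.2.2: "Analysis of PGD score will be performed separately at time 0 and at 24, 48 and 72 hours after ICU admission". Section 1.2 declares no changes from the protocol.

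**The concern.** The support rules exist because a ratio can look acceptable while the patient is being heavily supported. To apply them one must know the FiO2 the patient was actually on and whether nitric oxide was still running after 48 hours. The measurement procedure replaces the first with 1.0 in the study gas, and the medication rule drops the end of the second.

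The trial's objective is reduced PGD severity, and the PGD score is the endpoint that grades it. It is one of four secondary endpoints that receive inferential tests (Protocol synopsis and 9.4.3). If the less protected arm needs more support beyond 48 hours, grading on ratio and X-ray alone would under-grade that arm more often and shrink a true difference.

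**Working it through.** The plan states no figure on this point, so the check traces each rule to the data it needs.

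**1. When the rule is live.** It counts from transplant; visits count from ICU admission, which comes later. With the ±4 hour gas windows of Protocol Appendix 6, the earliest 72-hour gas falls 72 − 4 = 68 hours after ICU admission, always beyond 48 hours from transplant. The earliest 48-hour gas falls at 48 − 4 = 44 hours, so the rule is live at most but not necessarily all 48-hour visits.

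**2. FiO2 in use.** Protocol 7.5.1 and 7.5.2 list the ratio, X-ray, vital signs and cardiopulmonary measurements, not the FiO2 before the switch. SAP 3.1 mentions FiO2 as measured, but that belongs to the study gas and is 1.0 by design. The morning log in Protocol 7.5.3 records reasons for not weaning, not FiO2. Appendix 1 does not say which FiO2 its rules mean.

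**3. Nitric oxide.** Use in the operating room and a start date are captured. A start date clearly more than 48 hours after transplant would itself show use beyond 48 hours. For nitric oxide begun in the operating room or early in the ICU, the listed items do not show whether it continued past 48 hours.

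**4. Effect on the grade.** For a patient beyond 48 hours with infiltrates, where the trigger means ventilation at an FiO2 in use above 0.5, or nitric oxide:

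| Situation | SAP grade | Appendix 1 grade (FiO2 in use) |
|---|---|---|
| Trigger, ratio below 200 | 3 | 3 |
| Trigger, ratio 200 to below 300 | 2 | 3 |
| Trigger, ratio 300 or more | 1 | 3 |
| No trigger, FiO2 in use 0.3 to 0.5 | by ratio | by ratio |
| No trigger, FiO2 in use below 0.3, ratio below 300 | 2 or 3 | 1 |

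Under-grading is confined to rows two and three. The last row goes the other way. Without infiltrates the SAP gives grade 0. If the trigger is met, Appendix 1 gives both 0 and 3 and states no precedence.

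**5. Size.** No document figure gives the share still supported, so this is an illustration on assumptions. Number under-graded = 100 × v × u × q, where

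- v is the share still supported beyond 48 hours (assumed 0.10 to 0.40);
- u is the share of those meeting the trigger (assumed 0.25 to 1.00);
- q is the share of those with infiltrates and a ratio of at least 200 (assumed 0.25 to 0.84).

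The upper q uses the 24-hour mean and SD in Protocol 9.1 under a normal model: (200 − 315)/117 = −0.983, so 16.3% lie below 200 and about 84% at or above. It treats everyone as having infiltrates and may not apply at 48 to 72 hours.

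- Low: 100 × 0.10 × 0.25 × 0.25 = 0.6
- Middle: 100 × 0.20 × 0.50 × 0.50 = 5.0
- High: 100 × 0.40 × 1.00 × 0.84 = 33.6

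A range of about 1 to 34 patients shows that the documents do not settle the size.

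**The case against.** The CRF is not among the documents and may hold a ventilator FiO2 field; what can be shown is only that the protocol's lists do not name one. Neither document says whether the site assigns the grade or a program derives it. A site grading at the bedside would know the current FiO2 and nitric oxide status. Additional standard-of-care ratios are recorded for patients with clinically diagnosed PGD, and nitric oxide is not unrecorded, since use and start are captured. The score is a secondary, exploratory endpoint.

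These points narrow the finding but do not remove it. Bedside grading would still leave open which FiO2 a center applied. Clinical PGD requires an episode consistent with grade 3 on ratio and X-ray (Protocol 7.5.2), so the extra ratios are not required for a patient whose ratio stays at or above 200.

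A reader might infer that everyone still ventilated at 48 or 72 hours becomes grade 3, because the study-gas FiO2 of 1.0 exceeds 0.5. For example, a patient on a clinical FiO2 of 0.4 with a ratio of 350 and infiltrates would move from grade 1 to grade 3. The documents do not support this. The SAP derivation has no such rule, so that patient is grade 1 in the planned analysis. Protocol 7.5.2 also separates the FiO2 a patient is on from the five-minute setting for the gas.

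**Conclusion.** The concern holds in this form: from the items the protocol lists, the FiO2 and nitric oxide rules of Appendix 1 cannot be reliably applied to patients still supported beyond 48 hours. The SAP drops both rules while declaring no departure from the protocol. The result is under-grading at 48 and 72 hours of patients with infiltrates and a ratio of 200 or more who meet the trigger.

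A reader might go further and conclude that the 48- and 72-hour grades are wrong in general. They are not: patients with infiltrates and a ratio below 200 are grade 3 either way, and supported patients with FiO2 in use between 0.3 and 0.5 and no nitric oxide keep their threshold grade. Nor is the effect on clinical recovery (grade 1 or less) a strong point, because the extra PGD data feed listings (SAP 4.11.2 to 4.11.4 and 4.17.2), not a planned test.

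The number affected is unknown. The primary analysis of PaO2/FiO2 at 0 and 24 hours is untouched. The conclusion assumes that the CRF has no fields beyond those the protocol names. If it has them, the unclear choice of FiO2, the unstated precedence and the SAP omission remain.

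**What to change.** 1. Unless the CRF already holds them, record at each PGD time point the FiO2 in use just before the switch and nitric oxide yes/no, plus nitric oxide start and stop date and time. Retrieve the same items from ICU charts for patients already enrolled (about 60 when this SAP version was written, SAP 1.1).
2. In Protocol 14.1.1, state that the rules for FiO2 above 0.5 and below 0.3 use the pre-switch value and that the ratio thresholds use the study gas. State the precedence between the no-infiltrate rule and the grade-3 override.
3. Put the same rules into the PGD derivation in SAP Section 5, or declare their omission in SAP 1.2. Steps 1 and 2 alone would not change a grade derived by the SAP's present definitions.

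The cost is a few CRF fields, a one-off abstraction of routinely charted values before the Month 1 database lock, and short text changes. No new procedure or change in care is needed.
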